## 6.3 Exploratory Efficacy Endpoints and Analyses

- Change from baseline in inflammatory biomarkers specifically: IL-6; D-dimer; ferritin; CRP; interferon  $\gamma$  through Day 14 will be summarized for each treatment group by visit.
- Change from baseline in quantitative anti-SARS-CoV-2 IgM and IgG antibodies through Day 14 will be summarized for each treatment group by visit.
- Overall assessment of COVID-19 symptoms severity on Day 7 and Day 29 will be summarized for each treatment group by visit.

# 7. SAFETY ANALYSIS

Safety assessments will include assessment of AEs, chemistry, hematology (complete blood count and differential), COVID-19 clinical features, and vital signs. All safety summaries (or analyses if applicable) will be conducted using the SAF population. No formal hypothesis testing will be performed to compare differences between treatment groups.

## 7.1 Extent of Exposure and Compliance

The duration of infusion in minutes, total volume prepared, and total volume infused will be summarized by treatment group. For each syringe, the occurrence of dose interruption and whether 100% of study drug infused will also be summarized by treatment group. In addition, treatment compliance will be calculated and summarized for each treatment group. The summaries will include descriptive statistics of the treatment compliance as well as number and percentage of subjects with compliance between 80% and 120% in each treatment group.

Treatment compliance (%) will be calculated as follows:

(Total volume infused [mL] / Total volume prepared [mL]) x 100.

### 7.2 Adverse Events

All AEs and serious AEs (SAEs) occurring on Day 1 through the Day 29 ( $\pm 1$  day)/Final Visit must be fully recorded in the subject's medical record and eCRF, and SAE form (if serious). At the time of the Day 60 ( $\pm 2$  days) Phone Check any additional SAEs/non-serious AEs will also be collected and recorded. AEs will be classified by SOC and PT using the most recent version of MedDRA.

### 7.2.1 Treatment-emergent Adverse Events

For summary purposes, AEs will be classified as treatment-emergent AEs (TEAEs) or nontreatment-emergent AEs (non-TEAEs) depending on the comparison of AE onset date/time with the date/time of study drug administration. A TEAE will be defined as an AE which occurred on or after the date/time of study drug administration. For adverse events with incomplete start dates/times, the same imputation algorithm for missing or partial date/time information as described in Section 5.6 will be used for the determination of an AE being treatment emergent or not. Briefly, the unknown portions of an AE onset date/time will be imputed to the latest possible before being compared to the date/time of study drug administration.

Non-TEAEs will be summarized separately from TEAEs by SOC and PT for each treatment group and overall.

#### 7.2.2 Adverse Event Severity

Refer to the study protocol, Section 8.2.5.

#### 7.2.3 Adverse Event Relationship to IP

Refer to the study protocol, Section 8.2.4.

#### 7.2.4 Serious Adverse Events

Refer to the study protocol, Section 8.2.7.

#### 7.2.5 Adverse Event Summaries

All AEs (serious and non-serious) occurring from Day 1 through the end of study, regardless of relationship to IP, will be included and classified by SOC and PT using MedDRA.

For TEAEs, the following will be summarized and presented for the SAF population:

- i. An overall summary of TEAEs, which includes:
  - 1. the number and percentage of subjects experiencing a TEAE
  - 2. the number and percentage of subjects experiencing a TEAE by strongest relationship to IP
  - 3. the number and percentage of subjects experiencing a TEAE by greatest severity
  - 4. the number and percentage of subjects experiencing a TEAE with Grade  $\geq 3$
  - 5. the number and percentage of subjects experiencing a treatment-emergent SAE
  - 6. the number and percentage of subjects experiencing a TEAE leading to death
  - 7. the number and percentage of subjects experiencing a TEAE leading to study withdrawal
- ii. the number and percentage of subjects experiencing a TEAE by SOC and PT.
- iii. the number and percentage of subjects experiencing an adverse drug reaction (ADR; i.e., potentially related TEAE) by SOC and PT, where an ADR is defined as any TEAE with a causal relationship to IP assessed as 'Possibly Related' or 'Definitely Related'.
- iv. the number and percentage of subjects experiencing a TEAE by SOC, PT and the strongest relationship to IP
- v. the number and percentage of subjects experiencing a TEAE by SOC, PT and the greatest severity
- vi. the number and percentage of subjects experiencing a TEAE with Grade >=3 by SOC and PT
- vii. the number and percentage of subjects experiencing an ADR with Grade >=3 by SOC and PT
- viii. the number and percentage of subjects experiencing a treatment-emergent SAE by SOC and PT
- ix. the number and percentage of subjects experiencing a potentially related treatment-

CONFIDENTIAL

emergent SAE by SOC and PT

- x. the number and percentage of subjects experiencing a TEAE leading to death by SOC and PT
- xi. the number and percentage of subjects experiencing a TEAE leading to study withdrawal by SOC and PT

In the overall summary of TEAEs table (i), besides tabulating the number and percentage of subjects, the total number of TEAE episodes will also be provided. If a subject has repeated episodes of a particular TEAE, all episodes will be counted in the summary table.

In the remaining summary tables, the incidence of TEAEs will be calculated by dividing the number of subjects who have experienced the event by the total number of subjects. Thus, the incidence of TEAEs is shown in terms of the total number of subjects and not in terms of the total number of episodes. If a subject has repeated episodes of a particular TEAE, only the most severe episode, or the episode with the strongest causal relationship to IP, will be counted in the summary tables.

A subject with more than one type of TEAE in a particular SOC or PT will be counted only once in the total of subjects experiencing TEAEs in that particular SOC or PT.

All occurrences of all AEs and SAEs will be listed for each subject, grouped by treatment group. The listing will contain the following information: treatment group, verbatim term, SOC, PT, severity and grade (mild [Grade 1], moderate [Grade 2], severe [Grade 3], Life-threatening [Grade 4], Fatal [Grade 5]), relationship to IP, date/time and day of onset, date/time and day of resolution, action taken with regard to IP, whether additional non-drug or drug treatment was given to treat the adverse event, the outcome, whether the event was an SAE, whether it led to study withdrawal, whether it occurred during IP infusion, and whether it is a TEAE. Listings will be sorted by treatment group, subject identification number, onset date, SOC, and PT. If the onset date is completely missing, then these events will be presented first. If the onset date is missing a month or a day, then these events will be presented before any complete dates.

### 7.3 Clinical Laboratory Assessments

All routine laboratory analyses including serum chemistry (creatinine, albumin, ALT, total bilirubin, and LDH) and hematology (hemoglobin, hematocrit, platelet count, absolute neutrophil & lymphocyte count, leukocyte count with differential) will be conducted by a central laboratory.

Laboratory tests will be obtained at the time points presented in Appendix A. Continuous clinical laboratory values will be summarized by presenting descriptive statistics of raw data and change from baseline values at each time point for each treatment group, if feasible. Qualitative results at each time point measured will be summarized by presenting the number and percentage of subjects for each category. Shift tables, based on the high/low flags, will also be summarized by treatment group at each visit for all laboratory tests with normal ranges, when available.

When there are repeat scheduled measurements for a given visit, only the last measurement will be used in the table summaries.

Listings will include normal ranges and flags for values outside of the reference ranges, when available.

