# 8.3.8 Adverse Event Documentation

All AEs and SAEs occurring on Day 1 through the Day 29 (±1 day)/Final Visit must be fully recorded in the subject's medical record and CRF, and SAE report form (if serious).

At the time of the Day 60 (±2 days) Phone Check any additional SAEs/non-serious AEs will also be collected and recorded.

It is the responsibility of the investigator to ensure that AEs are appropriately recorded.

AEs will be collected through directly observed events or spontaneously volunteered by the subject. Clearly related signs, symptoms and abnormal diagnostic procedures should preferably be grouped together and recorded as a single diagnosis or syndrome wherever possible.

The following variables must be recorded:

- The verbatim term (a diagnosis is preferred)
- Date/time of onset
- Date/time of resolution
- Severity (mild, moderate, severe [Grade 3 to Grade 5])
- Causality (unrelated, possibly related, definitely related)\*
- Seriousness (yes, no)
- Action taken (with regard to IP)
- Other action (to treat the event)
- Outcome and sequel (follow-up on AE)

\*Causality assessment will be made only when the AE occurs after the subject has initiated at least one infusion of the IP. An AE occurring before subject's exposure to IP will be always labeled as "unrelated".

For AEs that occur during infusions, the infusion rate in effect at the time of onset of the AE, the time of onset of the AE and the time of AE change materially in intensity and/or resolve will be captured.

In addition to the investigator's own description of the AE, each AE will be encoded according to the Medical Dictionary for Regulatory Activities (MedDRA).

For example, a laboratory test abnormality considered clinically significant, eg, causing the subject to withdraw from the study, requiring treatment or causing apparent clinical manifestations, or judged clinically significant in the context of the subject's medical history by the investigator, should be reported as an AE.

Each event must be described in detail along with start and stop dates, severity, relationship to IP, action taken and outcome. Each event must be adequately supported by documentation as it appears in the subject's medical or case file.

[figure not shown]

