#### 2.2.4 Safety Endpoints

The safety endpoints include:

- Cumulative incidence of treatment-emergent serious adverse events (SAEs) and potentially related SAEs through Day 60 Phone Check.
- Cumulative incidence of Grade 3-5 treatment-emergent adverse events (TEAEs) and potentially related severe TEAEs through Day 29 as defined in the Common terminology Criteria for Adverse Events (CTCAE), US Department of Health and Human Services, National Institutes of Health (NIH), and National Cancer Institute (NCI) through Day 29.

- Cumulative incidence of all TEAEs and potentially related TEAEs through Day 29.
- Change from baseline in key biochemical parameters of organ function/dysfunction: ALT; LDH; absolute lymphocyte count; creatinine through Day 14.

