# 4. GENERAL CONSIDERATIONS FOR DATA ANALYSIS

Unless otherwise specified, continuous variables will be summarized using descriptive statistics (n, mean, standard deviation, median, minimum, and maximum). Categorical variables will be summarized showing the number and percentage of subjects within each category.

Summary results will be provided for each treatment group. All tabulations will be based on pooled data across centers.

All statistical tests will be two-sided and tested at the 5% level of significance.

Unscheduled visits will be excluded from the summaries but will be included in the data listings.

All p-values will be displayed to four decimal places, with p-values less than 0.0001 presented as '<0.0001'. Minimum and maximum values will be reported in the units of collection with 3 decimals being maximum value; the mean will be presented with 1 decimal place more and the standard deviation 2 decimal places more than the units of collection. Percentages for categorical summaries will be represented to 1 decimal place.

Analyses will be performed using SAS for Windows statistical software, version 9.4 or higher (SAS, Cary, NC), except where other software may be deemed more appropriate. In the event that other software is used to perform some analyses, the details will be provided in the Clinical Study Report.

will perform all efficacy and safety analyses described in this SAP and Grifols will review them.

Subject data will be listed, sorted by treatment group and subject number. When applicable, listings will be additionally sorted by visit and assessment date/time.

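### Laboratory shift tables built on high/low flags leave no count, by arm, of subjects with marked worsening that is independent of adverse-event reporting

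*SAP*

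**What the plan says.** SAP 2.2.4 names a laboratory safety endpoint: "Change from baseline in key biochemical parameters of organ function/dysfunction: ALT; LDH; absolute lymphocyte count; creatinine through Day 14". SAP 7.3 serves it with three outputs.

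- **Descriptive statistics:** "Continuous clinical laboratory values will be summarized by presenting descriptive statistics of raw data and change from baseline values at each time point", by treatment group. SAP 4 defines these as "n, mean, standard deviation, median, minimum, and maximum".
- **Shift tables:** "Shift tables, based on the high/low flags, will also be summarized by treatment group at each visit for all laboratory tests with normal ranges".
- **Listings:** "Listings will include normal ranges and flags for values outside of the reference ranges, when available".

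A separate route runs through adverse events. Protocol 8.3.8 says that "a laboratory test abnormality considered clinically significant, eg, causing the subject to withdraw from the study, requiring treatment or causing apparent clinical manifestations", or one judged clinically significant in light of the medical history, should be reported as an adverse event. SAP 7.2.5 then tabulates, among other things, "the number and percentage of subjects experiencing a TEAE with Grade >=3 by SOC and PT".

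The safety analysis is descriptive. SAP 7 states: "No formal hypothesis testing will be performed to compare differences between treatment groups". Neither document plans a laboratory table by CTCAE grade, by multiples of a reference limit, or by worst post-baseline value.

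**The concern.** A high/low flag gives three categories: low, normal and high. Above the upper limit, or below the lower one for lymphocytes, all sizes of abnormality are treated alike. A subject already out of range at baseline who becomes much worse stays in the same category and is counted as unchanged.

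Organ toxicity often shows as large changes in a few subjects rather than as a shift of the whole arm. The first question a safety reader asks is how many subjects in each arm worsened markedly. This matters more than usual here. Protocol 2.2 says there is no clinical experience with the product so far, and with no safety testing planned, the descriptive tables are the only comparison between arms. High baselines are possible: the exclusion criteria set no laboratory limits, and chronic kidney disease is a recorded comorbidity and a planned subgroup.

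**Working it through.** The documents give no figure on this point, so there is nothing to reproduce.

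**Inputs.** The planned arm size is 267, or about 240 before the allowance for 10% withdrawal (Protocol 9.2, SAP 10). The documents give no reference limits. Values below are multiples of ULN, with a lower limit of 0.2 x ULN assumed for illustration. The sharing of cells does not depend on the particular limits.

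**Check 1: the flag rule applied to pairs of values.**

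| Baseline | Post-baseline | Fold change | Shift-table cell |
|---|---|---|---|
| 0.98 | 1.02 | 1.04 | Normal to high |
| 0.98 | 9.8 | 10 | Normal to high |
| 0.5 | 5.0 | 10 | Normal to high |
| 1.10 | 1.15 | 1.05 | High to high |
| 1.10 | 11.0 | 10 | High to high (no shift) |
| 0.5 | 0.6 | 1.2 | Normal to normal |

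Rises of very different size share a cell when both cross the limit, or when both subjects were already high. A small rise that stays within range falls in a different cell.

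**Check 2: what the other summary statistics would show.** Suppose two of 267 subjects rise from 1.2 to 10 x ULN and the rest do not change.

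- Mean change: 2 x (10 - 1.2)/267 = 17.6/267 = 0.066 x ULN.
- SD of change: sqrt(2 x 8.8^2/267) = sqrt(0.58) = about 0.76 x ULN. If the other subjects have an SD of 0.3 x ULN (assumption), it is about sqrt(0.09 + 0.58) = 0.82 instead of 0.30.
- Maximum change: 8.8 x ULN. Raw maximum: 10 x ULN.
- Shift table: two subjects in high to high, so no shift.

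A single subject rising by 9 x ULN moves the mean by 9/267 = 0.034 x ULN, or 9/240 = 0.038 x ULN. The mean and the shift table hide these changes; the maximum and SD reveal that something happened.

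**Check 3: whether those statistics give a count.** Suppose one subject, or five, rise by 8.8 x ULN and the rest do not change. The maximum change is 8.8 in both cases. The SD is sqrt(8.8^2/267) = 0.54 in the first and sqrt(5 x 8.8^2/267) = 1.20 in the second. The SD responds, but it mixes the number affected with the size of the changes and the background spread, so it cannot be read back as a number of subjects.

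**Check 4: whether the maximum always captures the peak.** SAP 4 leaves unscheduled visits out of the summaries, and SAP 7.3 uses only the last of repeated scheduled measurements. Protocol 5.3.4 places the Day 14 assessments of a withdrawing subject at an unscheduled visit. A peak value could therefore appear in the listings but in no table.

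**The case against.** The strongest reply is that the plan already reports magnitude. The endpoint is change from baseline, and SAP 7.3 summarizes exactly that by arm and visit; the shift table is an addition. In the worked example, the same output that shows a small mean change also shows a maximum change of at least 8.8 x ULN and an inflated SD. The listings give every value. A ten-fold rise is the kind of finding that the adverse-event route is meant to catch, and SAP 7.2.5 then counts subjects by arm, severity and grade. There are only two scheduled post-baseline laboratory visits, Day 7 and Day 14, and both are tabulated.

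Most of this stands. A reader might infer that the plan loses the size of laboratory changes, or that the safety endpoint cannot be assessed. The documents do not support either reading. Nor do they support saying that any trivial rise shares a cell with a ten-fold rise; Check 1 shows the conditions.

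A reader might also suppose that a known share of subjects sits in the high-to-high cell. If 5% to 30% were high at baseline, that would be 0.05 x 267 = 13 to 0.30 x 267 = 80 subjects per arm. That range is an assumption with no figure behind it in the documents, and entrants are asymptomatic outpatients with NEWS of 2 or less.

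What the reply does not supply is the count. The maximum describes one value per arm and visit. The listings would have to be tallied by hand over about 801 subjects. The adverse-event tables depend on the investigator judging an abnormality clinically significant, with no numeric threshold. Protocol 8.3.5 also separates mild from moderate events by their effect on normal activities, so a symptomless rise need not be classed by its size.

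**Conclusion.** The point holds as a minor reporting gap. The flag-based shift table is a stated method, not an error, and no passages conflict. Its limits follow from the rule itself. Rises of very different size that cross a limit share one cell, and a subject already beyond a limit at baseline shows no shift however much further the value moves. Other planned outputs preserve the magnitude, but none counts by arm the subjects who worsened markedly, independently of adverse-event reporting.

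The numerical examples rest on assumed values and on no change, or an assumed spread, in the remaining subjects. The missing count does not rest on them. The gap has no bearing on the primary analysis, the type I error rate, power or sample size.

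**What to change.** In SAP 7.3, add a table by arm of baseline category against worst post-baseline category over Day 7 and Day 14 for ALT, LDH, absolute lymphocyte count and creatinine. The flag-based table can stay.

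- Use CTCAE grade where the analyte has a graded scale, since the trial already uses CTCAE for adverse events. Otherwise use prespecified multiples of the central-laboratory limit. For LDH, one illustrative set is up to 1, above 1 to 2, above 2 to 3, above 3 to 5, above 5 to 10, and above 10 x ULN.
- For each analyte separately, give the number and percentage of subjects who worsen by two or more categories. Do not pool across analytes, because the category scales differ.
- State that repeat and unscheduled values count towards the worst value, as an explicit exception to the SAP 4 rule on unscheduled visits and the SAP 7.3 rule on repeat measurements.

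The central-laboratory values are already collected, so no new data or visits are needed. The cost is a short SAP edit, a little programming and slightly larger tables.

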### 7.4 Vital Signs

Descriptive summaries of the vital signs (both raw and change from baseline values) including systolic and diastolic blood pressure, pulse, respiratory rate, and body temperature will be prepared for each treatment group by visit.

Qualitative results including clinically significant change from baseline (no/yes) will be summarized by presenting the number and percentage of subjects for each category at each post-baseline time point.

### 8. DSMB ANALYSIS

An independent DSMB will review interim safety data when approximately 399 patients have been randomized and treated with follow-up through Day 29 (approximately 133 patients per randomized group).

The DSMB's specific activities will be defined by a mutually agreed charter, which will define the DSMB's membership, conduct and meeting schedule.

### 9. INTERIM FUTILITY ANALYSIS

An interim analysis will be conducted in the December 2021 timeframe based on all available data assessable for the primary endpoint and key secondary efficacy endpoints to assess whether the trial will be terminated due to lack of efficacy (futility). The unblinded output will be reviewed by an independent unblinded team, and the study team will remain blinded.

The decision for the interim analysis will be based on the conditional power (the power conditional on the observed data accumulated at the interim analysis) for the primary outcome, as well as assessment of the secondary efficacy outcomes.

The futility analysis will include for the primary efficacy endpoint variable, all patients with data through Day 14, and for the following secondary efficacy endpoint variables, all patients with data through Day 14 or Day 29, as specified for each endpoint:

- Time to COVID-19 symptoms specifically defined as the time to fulfillment of the case definition used for the primary efficacy variable through Day 14.
- Proportion of subjects who remain in an outpatient setting and maintain SpO2 ≥94% on room air on Day 3, Day 7, and Day 14.
- Proportion of subjects who require O2 supplementation on or before Day 29.
- If requiring supplemental oxygen post randomization: Duration of any oxygen through Day 29.
- Absolute value and mean change from baseline in the 7-point Ordinal scale at Day 1, Day 7, Day 14, and Day 29
- Proportion (percentage) of subjects in each severity category of the 7-point Ordinal scale at Day 1, Day 7, Day 14, and Day 29.
- Assessment of Clinical Severity: Change in NEWS from baseline (at Day 7, Day 14, and

Day 29).

- Proportion who require at least one COVID-19 related medically attended visit for management/treatment of COVID-19 (apart from routinely scheduled study-directed visits) which may occur in any setting through Day 29 (e.g., Emergency department, urgent care, outpatient clinic or professional setting wherein direct in-person/telemedicine medical assessment and escalation of care for COVID-19 is provided by licensed healthcare personnel).
- Proportion of subjects who require hospital admission for medical care (non-quarantine purposes) through Day 29.
- If admitted to hospital post randomization: Duration of hospital stay through Day 29.
- Proportion of subjects who require ICU admission or initiation of ICU-level care\* through Day 29.
- If admitted to ICU post randomization: Duration of ICU stay through Day 29.
- Proportion of subjects requiring invasive mechanical ventilation through Day 29.
- If requiring invasive mechanical ventilation post randomization: Duration of invasive mechanical ventilation through Day 29.
- All-cause mortality through Day 29.
- Incidence of critical COVID-19 illness, defined as any one of the following: (a) requiring ICU admission or ICU level of care\*, (b) invasive mechanical ventilation, or (c) resulting in death by Day 29.
- Length of time to clinical progression to critical COVID-19 illness through Day 29 (defined as the time to death, invasive mechanical ventilation, or ICU admission/requiring ICU level of care).

After this interim analysis, the 1 gram dose arm may be terminated, the trial may be terminated (if the 2 gram dose is discontinued, the 1 gram dose will also be terminated), or the study will continue as originally planned unless discontinued for business or feasibility reasons in a setting of changing epidemic dynamics in the geographic catchment of the trial.

The futility analysis will not inflate the type I error since the trial will not be stopped to claim efficacy. The primary and key secondary efficacy outcomes will be analyzed using the methods described above in Section 6.1 and 6.2. No subgroup or sensitivity analyses are planned for the futility analysis.

Suppose at the time of data-cut for the futility analysis,  $x_0$  subjects meet the primary efficacy endpoint among  $m_0$  subjects in the placebo group, and  $x_1$  subjects have events among  $m_1$  subjects in the treatment group (1 gram or 2 grams C19-IG 20%). Let  $\tilde{p}_g = x_g/m_g$  for group g = 0, 1; and  $\tilde{p} = (x_0 + x_1)/(m_0 + m_1)$ .  $Z_1 = \frac{\tilde{p}_1 - \tilde{p}_0}{\sqrt{(m^{-1} + m^{-1})\tilde{p}(1 - \tilde{p})}}$  is the z-score corresponding to the Chi-

square statistic.

Let the final sample size be  $n_0$  and  $n_1$  in the placebo and treated (1 gram or 2 grams C19-IG 20%)

0

1

groups respectively. Let  $Z_{1-\alpha/2}$  be the 1-  $\alpha/2 = 97.5\%$  percentile of the normal distribution, which

can be calculated as the PROBIT function in SAS. Let  $t = (n_0^{-1} + n_1^{-1})/(m_0^{-1} + m_1^{-1})$ . The conditional power (CP) for the primary efficacy endpoint (each of C19-IG 20% dose groups compares to placebo) will be calculated using the formula:

$$CP = 1 - \Phi \left( \frac{Z_{1-\alpha/2} - Z_1/\sqrt{t}}{\sqrt{1-t}} \right)$$

where  $\Phi$  is the cumulative distribution function (CDF) for N(0,1).

